Appendix B. TOXICITY TABLE

Clinical Adverse Events			
VITAL SIGNS	Mild (Grade 1)	Moderate (Grade 2)	Severe Grade 3
Fever - °C	38.0-38.4	38.5-38.9	>38.9
Tachycardia - bpm	101-115	116-130	>130 or ventricular dysrhythmias
Bradycardia – bpm • Baseline ≥60 OR, if Baseline <60	• 50-54 OR, if Baseline <60, • 45-50	• 45-49 OR, if baseline <60, • 40-44	• <45 OR, if baseline <60 • <40
Hypertension (systolic) - mmHg	141-150	151-160	>160
Hypertension (diastolic) - mmHg	91-95	96-100	>100
Hypotension (systolic) - mmHg	85-89	80-84	<80
Tachypnea – breaths per min	23-25	26-30	>30
CARDIOVASCULAR	Mild (Grade 1)	Moderate (Grade 2)	Severe Grade 3)
Arrhythmia		Asymptomatic; transient signs; no medical intervention required	Recurrent/persistent; symptomatic medical intervention required
Hemorrhage, Blood Loss	Estimated blood loss ≤100 mL	Estimated blood loss >100 mL; no transfusion required	Transfusion required

QTc (Fridericia's correction) ¹	Asymptomatic, QTc interval 450-479 msec	Asymptomatic; QTc interval 480 to 499 msec OR Increase in interval 30-59 msec above baseline	Asymptomatic; QTc interval \geq 500 msec OR Increase in interval \geq 60 msec above baseline
PR Interval (prolonged) ¹	PR interval 0.21-0.25 sec	PR interval >0.25	Type II 2 nd degree AV block OR Ventricular pause >3.0 sec
RESPIRATORY	Mild (Grade 1)	Moderate (Grade 2)	Severe (Grade 3)
Cough	Transient; no treatment	Persistent cough	Interferes with daily activities
Bronchospasm, Acute	Transient; no treatment; FEV1 71-80% of predicted peak flow	Requires medical intervention; normalizes with bronchodilator; FEV1 60-70% of predicted peak flow	No normalization with bronchodilator; FEV1 $<60\%$ of predicted peak flow
Dyspnea	Does not interfere with usual and social activities	Interferes with usual and social activities; no treatment	Prevents daily and usual social activity OR requires treatment
GASTROINTESTINAL	Mild (Grade 1)	Moderate (Grade 2)	Severe (Grade 3)
Nausea	No interference with activity	Some interference with activity	Prevents daily activities
Vomiting	No interference with activity OR 1-2 episodes/24 hours	Some interference with activity OR >2 episodes/24 hours	Prevents daily activity OR requires IV hydration OR requires medical intervention

¹Inclusion dependent upon protocol requirements.

Diarrhea	2-3 loose or watery stools or <400 g/24 hours	4-5 loose or watery stools or 400-800 g/24 hours	≥6 loose or watery stools or >800g/24 hours OR requires IV hydration OR requires medical intervention
REACTOGENICITY			
LOCAL REACTIONS	Mild (Grade 1)	Moderate (Grade 2)	Severe (Grade 3)
Pain – experienced without touching the injection site (spontaneous discomfort)	Does not interfere with activity	Repeated use of non-narcotic pain reliever >24 hours OR interferes with activity	Any use of narcotic pain reliever OR prevents daily activity
Tenderness – hurts only when injection site is touched, or the arm is moved	Discomfort only to touch	Discomfort with movement	Significant discomfort at rest
Pruritus (Itching)	Does not interfere with daily activity	Interferes with daily activity	Prevents daily activity
Ecchymosis (Bruising)*	Does not interfere with daily activity	Interferes with daily activity	Prevents daily activity
Erythema (Redness)*	Does not interfere with daily activity	Interferes with daily activity	Prevents daily activity
Induration (Hardness)/Swelling*	Does not interfere with daily activity	Interferes with daily activity	Prevents daily activity
Nodule	Does not interfere with daily activity	Interferes with daily activity	Prevents daily activity
Ulcer	Does not interfere with daily activity	Interferes with daily activity	Prevents daily activity
Ecchymosis (Bruising)*	25 mm – 50 mm	51 mm – 100 mm	>100 mm

Erythema (Redness)*	25 mm – 50 mm	51 mm – 100 mm	>100 mm
Induration (Hardness)/Swelling*	25 mm – 50 mm	51 mm – 100 mm	>100 mm
Nodule	25 mm – 50 mm	51 mm – 100 mm	>100 mm
Ulcer	1 mm – 50 mm	51 mm – 100 mm	>100 mm
SYSTEMIC REACTIONS	Mild (Grade 1)	Moderate (Grade 2)	Severe (Grade 3)
Allergic Reaction	Pruritus without rash	Localized urticaria OR requires oral therapy	Generalized urticaria; angioedema OR anaphylaxis OR requires epinephrine
Headache	No interference with activity	Repeated use of non-narcotic pain reliever >24 hours OR some interference with activity	Significant; any use of narcotic pain reliever OR prevents daily activity OR requires triptans
Fatigue	No interference with activity	Some interference with activity	Significant; prevents daily activity
Myalgia	No interference with activity	Some interference with activity	Significant; prevents daily activity
All Other conditions	Mild (Grade 1)	Moderate (Grade 2)	Severe (Grade 3)
Illness or clinical AE (as defined according to applicable regulations)	No interference with activity	Some interference with activity not requiring medical intervention	Prevents daily activity and requires medical intervention

*Will not be used as halting criteria.

Laboratory and Vital Signs Reference Ranges, Eligibility Ranges, and Toxicity Grading

Laboratory Adverse Events*	Mild	Moderate	Severe
	(Grade 1)	(Grade 2)	(Grade 3)
Blood, Serum, or Plasma			
Sodium (hyponatremia) – mEq/L	131-132	129-130	<129
Sodium (hypernatremia) – mEq/L	144 – 145	146 – 147	>147
Potassium (hyperkalemia) – mEq/L	5.2 – 5.4	5.5 – 5.6	>5.6
Potassium (hypokalemia) – mEq/L	3.2-3.4	3.0 – 3.1	<3.0
Glucose (hypoglycemia) – mg/dL	65 – 69	55 – 64	<55
Glucose (hyperglycemia) – mg/dL Fasting	106 – 125	126 – 200	>200
Blood Urea Nitrogen – mg/dL	21-26	27 – 31	> 31
Creatinine (Male) – mg/dL	1.3 – 2.0	2.1-2.3	>2.3
Creatinine (Female) – mg/dL	1.0 – 1.7	1.8 – 2.0	>2.0
Calcium (hypocalcemia) – mg/dL	8 - <LLN	7.5 – 7.9	<7.5
Calcium (hypercalcemia) – mg/dL	ULN - 10.8	10.9 – 11.4	>11.4
CK-U/L	309-1000	1001-1500	>1500
Albumin (hypoalbuminemia) – g/dL	2.8 – 3.4	2.5 – 2.7	< 2.5
AST – U/L (Male)	40-97	98-195	>195
AST – U/L (Female)	32-77	78-155	>155
ALT – U/L (Male)	41-100	101-200	>200
ALT – U/L (Female)	33-80	81-160	>160

Laboratory Adverse Events*	Mild	Moderate	Severe
	(Grade 1)	(Grade 2)	(Grade 3)
Alkaline phosphatase – IU/L (Male)	131-260	261-390	>390
Alkaline phosphatase – IU/L (Female)	106-210	211-315	>315
Total Bilirubin (serum) – mg/dL	1.3-1.5	1.6-1.9	>1.9
Direct Bilirubin – mg/dL	NA	NA	NA
Chloride –mEq/L (hypochloremia)	NA	NA	NA
Chloride –mEq/L (hyperchloremia)	NA	NA	NA
CO2 –mEq/L (hypo)	NA	NA	NA
CO2 –mEq/L (hyper)	NA	NA	NA
Total Protein – g/dL	5.5 - 5.9	5.0 - 5.4	<5.0
Phosphorus- mg/dl (hypo)	2.3-2.4	2.1-2.2	<2.0
Phosphorus-mg/dl (hyper)	NA	NA	NA
Hemoglobin (Male) – g/dL	11.2 - 12.2	10.0 – 11.1	<10.0
Hemoglobin (Female) – g/dL	9.8 - 10.8	8.5 - 9.7	<8.5
WBC Increase – cell/mm ³	10,001– 15,000	15,001 – 20,000	> 20,000
WBC Increase – cell/mm ³ (African America Males)	9,001 – 14, 000	14,001 – 19, 000	>19,000
WBC Increase – cell/mm ³ (African American Females)	11,001 – 15,000	15,001 – 20,000	>20,000
WBC Decrease – cell/mm ³	2,500– 3,999	1,500 – 2,499	< 1,500
WBC Decrease – cell/mm ³ (African American Males)	2,200 – 2,499	1,200 – 2,199	<1,200
WBC Decrease – cell/mm ³ (African American Females)	2,200 – 2,499	1,500 – 2,199	<1,500

Laboratory Adverse Events*	Mild	Moderate	Severe
	(Grade 1)	(Grade 2)	(Grade 3)
Neutrophils Decrease – cell/mm ³	1,300 – 1,699	1,000 – 1,299	< 1,000
Neutrophils Decrease – cell/mm ³ (African American Males)	1,000 – 1,299	800 - 999	<800
Neutrophils Decrease – cell/mm ³ (African American Females)	1,100 – 1,299	1,000 – 1,099	<1,000
Platelets Decreased – 10 ³ /mm ³	120 – 149	100 – 119	<100
Hematocrit (Male) - %	33.0 -36.1	29.8 - 32.9	< 29.8
Hematocrit (Female) - %	29.5 - 32.6	26.0 – 29.4	< 26.0
RBC (Male) – x 10 ⁶ /uL	3.9 - 4.1	3.4 - 3.8	< 3.4
RBC (Female) – x 10 ⁶ /uL	3.5 - 3.7	3.0 - 3.4	< 3.0
Lymphocytes - cell/mm ³ decrease	600- 799	500 – 599	< 500
Monocytes – cell/mm ³ increase	1001-2000	2001-3000	>3000
Eosinophils - cell/mm ³ increase	871 - 950	951 - 1700	>1700
Basophils - cell/mm ³ increase	101 - 300	301 - 800	> 800
PT (prothrombin time) – seconds	11.6-12.6	12.7-13.7	>13.7
PT INR (Prothrombin INR)	1.2-1.4	1.5-1.9	2.0 or higher
PTT (partial thromboplastin time) –seconds	30.1-36.8	36.9-43.6	>43.6
Urine			
Protein	1+	2+	>2+
Glucose	1+	2+	>2+
Blood (microscopic) - red blood cells per high power field (rbc/hpf)**	3-10*	11-50*	>50 and/or gross blood**

Laboratory Adverse Events*	Mild	Moderate	Severe
	(Grade 1)	(Grade 2)	(Grade 3)
*Abnormal laboratory values, performed as part of hematology, chemistry panel, or urinalysis but not listed in Appendix B , will be evaluated by the study clinicians, recorded in the source document and, if clinically significant, considered AEs and graded according to the criterion described in Section 8.1 .

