8.7.2 Dose Escalation Halting Rules

Sentinel Subject Halting Rules

If any of the criterion below are met, the cohort will be suspended (enrollment and dosing), and the SMC ad hoc meeting will convene:

- Any SAE (regardless of the relationship to the study drug) through 48 hours post study drug administration.
- Any Grade 2 (or higher) adverse event deemed to be related to the study medication by the PI, having an initial onset within the first 72 hours post study drug administration that does not resolve within 72 hours from onset.
- Any subject experiences skin ulceration of any grade at an injection site.

Cohort Dose Escalation Halting Rules

If any of the criterion below are met, the escalation to the next cohort will be suspended (enrollment and dosing), and the SMC ad hoc meeting will convene.

- 2 or more subjects in a cohort experience the same grade 2 (or higher) related AE (laboratory or systemic) which is coded in the same HLTG per MedDRA coding, through Day 30 (SAD) or Day 30 (MAD) of the study.

- Two or more subjects within a cohort with post-dose QTcF > 500 or change from baseline >60 ms.
- Any subject experiences skin ulceration of any grade at an injection site.

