The following laboratory parameters will be presented (in order):

- Chemistry (CHEM): sodium, potassium, calcium, phosphorus, chloride, total carbon dioxide, glucose, blood urea nitrogen, creatinine, total cholesterol, low-density lipoprotein cholesterol, high-density lipoprotein cholesterol, triglycerides, total protein, albumin, aspartate aminotransferase (AST), alanine aminotransferase (ALT), alkaline phosphatase, total bilirubin, direct bilirubin, creatine phosphokinase. Total cholesterol, low-density lipoprotein cholesterol, high-density lipoprotein cholesterol, and triglycerides parameters were removed after Protocol v3.0. Only Cohort 1 subjects have results for the specified parameters. Due to limited number of subjects with available results, total cholesterol, low-density lipoprotein cholesterol, high-density lipoprotein cholesterol, and triglycerides will only be presented in [Table 21](#) and [Listing 11](#) and will be excluded from the change from baseline figures.
- Hematology (HEM): hemoglobin, hematocrit, RBC count, WBC count, neutrophil count, lymphocyte count, monocyte count, eosinophil count, basophil count, platelet count.
- Coagulation (COAG): prothrombin time, activated PTT, INR
- Urinalysis (UA): protein, glucose, occult blood.

By protocol, microscopic evaluation of urine or complete urinalysis is only performed if dipstick urinalysis is positive for blood. If complete UA or microscopic results were obtained in the absence of an abnormal dipstick result (or without dipstick tests being done), results of the complete UA or microscopy will still be summarized. Results determined using both methods will be listed. In tables, dipstick results will be presented prior to complete UA or microscopy results.

Laboratory parameters that have grading criteria for both decreases (result lower than normal range) and increases (result higher than normal range) will be summarized separately by direction of change. For example, sodium will be summarized separately as “Sodium, Decrease” and “Sodium, Increase.”

In tables summarizing toxicity grading, maximum severity observed after dosing will be summarized (max severity post-baseline, including unscheduled visits) for each parameter. Results of maximum severity for “Any Parameter” will be included for all clinical laboratory results. For “Any Parameter” results, the maximum severity across all laboratory parameters in the respective category is summarized by time point.

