#### 14.3.4 Abnormal Laboratory Value Listings (by Subject)

**Table 16: Listing of Abnormal Laboratory Results – Chemistry**

[Implementation Note: This listing is included in the table shells document, as it is included in the body of the abbreviated CSR. This listing includes all abnormal Chemistry results (laboratory results outside of the normal range defined in the protocol). Normal chemistry results for other parameters that occurred on the same visit as the abnormal result will not be listed. There is a separate, complete listing of all Chemistry results. In the Laboratory Parameter column, indicate the units (LB.LBSTRESU) after the parameter, e.g., Sodium (mEq/L). This listing is not color-coded. Results that are outside the normal range but not mild, moderate, or severe will have ONR listed as severity. Similarly, results that meet grading criteria of mild, moderate, or severe but which are not treatment emergent (not worse than baseline) will be shown as ONR.]

Sort order: Dose Group, Subject ID, Time Point, and Parameter.]

Dose Group	Subject ID	Sex	Time Point	Date of Assessment	Laboratory Parameter (Units)	Result	Severity

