## 14.3.5 Displays of Laboratory Results

### 14.3.5.1 Chemistry Results

**Table 20: Chemistry Toxicity Grade by Parameter, Severity, Dose Group, and Time Point**

[Implementation Note: Severity will be graded based on toxicity criteria in protocol. If there is not at least 1 Mild, Moderate, or Severe Event for Max Severity Post-Baseline, then only the Max Severity Post-Baseline row will be shown for the parameter. Toxicities representing an increase in the laboratory result will be summarized separately from decreases.]

Dose Group	Time Point	N	Mild	Moderate	Severe
			n (%)	n (%)	n (%)
Any Parameter					
SAD Any Dose	Baseline	x	x (x)	x (x)	x (x)
	Max Severity Post-Baseline	x	x (x)	x (x)	x (x)
	Day 2	x	x (x)	x (x)	x (x)
	Day 7	x	x (x)	x (x)	x (x)
	Final Visit	x	x (x)	x (x)	x (x)
SAD 1 mg	Baseline	x	x (x)	x (x)	x (x)
	...	x	x (x)	x (x)	x (x)
SAD 10 mg	Baseline	x	x (x)	x (x)	x (x)
	...	x	x (x)	x (x)	x (x)
Placebo	Baseline	x	x (x)	x (x)	x (x)
	...	x	x (x)	x (x)	x (x)
Sodium, Decrease					
SAD Any Dose	Baseline	x	x (x)	x (x)	x (x)
...	...	x	x (x)	x (x)	x (x)
Notes: The “Max Severity Post Baseline” rows indicate the maximum severity experienced by each subject at any time point post baseline, including unscheduled assessments.					
N=Number of subjects in the Safety Population with the laboratory result assessed at the respective time point.					

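### Protocol Appendix B gives a phosphorus of exactly 2.0 mg/dL no grade, although 2.1 is Grade 2 and 1.9 is Grade 3, so the SAP's graded summary would not count it

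*Protocol*

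**What the plan says.** Protocol Appendix B prints the low-phosphorus row, labelled "Phosphorus- mg/dl (hypo", as "Phosphorus- mg/dl (hypo) 2.3-2.4 2.1-2.2 <2.0", for Grades 1, 2 and 3 in turn. The low-potassium row of the same table, also printed to one decimal, reads "Potassium (hypokalemia) – mEq/L 3.2-3.4 3.0 – 3.1 <3.0".

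Phosphorus is an analysed chemistry parameter. SAP Section 7.6 lists "sodium, potassium, calcium, phosphorus, chloride, total carbon dioxide, glucose" among the results to be presented. The note to SAP Table 20 says "Severity will be graded based on toxicity criteria in protocol", and that table has columns for Mild, Moderate and Severe only. The note to Table 16 covers abnormal results without a grade: "Results that are outside the normal range but not mild, moderate, or severe will have ONR listed as severity". Listing 11 follows the same convention.

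Grades are also used in the conduct of the trial. The cohort escalation rule in Protocol Section 8.7.2 counts subjects with the "same grade 2 (or higher) related AE (laboratory or systemic") within one MedDRA high-level group term. Protocol Section 10.5.2 defines a treatment-emergent laboratory abnormality by a change of grade.

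**The concern.** A grading scale should give every reportable abnormal value a grade, and the grade should not improve as the value worsens. This row fails both tests at one point. Going down from 2.4, the grade rises from 1 to 2, disappears at 2.0, and returns as 3 at 1.9.

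A grading program that follows the table literally would give 2.0 no grade. At stake is the Table 20 count for phosphorus, and through it the row for any chemistry parameter. A subject whose worst value is 2.0 would be counted at a milder grade reached at another visit, or at none. If nobody else had a graded low phosphorus, the Table 20 note would also suppress that parameter's time-point rows. Under the grade-based definition in Protocol Section 10.5.2, a fall from normal to 2.0 would not be treatment-emergent, whereas a fall to 2.1 would be.

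**Working it through.** There is no sample size or error rate to reproduce. The check applies the printed limits at the printed precision.

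**Inputs.** Appendix B low phosphorus: Grade 1 if 2.3 ≤ x ≤ 2.4; Grade 2 if 2.1 ≤ x ≤ 2.2; Grade 3 if x < 2.0. The step is 0.1 mg/dL, the precision of the printed limits.

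| Phosphorus (mg/dL) | Grade as written | Grade 3 changed to ≤ 2.0 | Grade 2 changed to 2.0-2.2 |
|---|---|---|---|
| 2.4 | 1 | 1 | 1 |
| 2.3 | 1 | 1 | 1 |
| 2.2 | 2 | 2 | 2 |
| 2.1 | 2 | 2 | 2 |
| 2.0 | none | 3 | 2 |
| 1.9 | 3 | 3 | 3 |

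The value 2.0 fails the Grade 2 test because 2.0 < 2.1, and fails the Grade 3 test because 2.0 is not below 2.0. Either way of closing the gap makes it at least Grade 2.

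**Is this a convention of the table?** The same test was run in exact decimals on 41 numeric laboratory rows (21 decrease, including phosphorus, and 20 increase). For low calcium, a lower limit of normal of 8.5 was assumed. Phosphorus was the only row with a gap; the other 40 are contiguous. For example, low potassium Grade 2 ends at 3.0 and Grade 3 is below 3.0; total protein Grade 2 ends at 5.0 and Grade 3 is below 5.0. Five further rows, read directly, are also contiguous: high calcium, the two WBC-increase rows for African American subjects, INR and microscopic urine blood.

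**Does another version close it?** SAP Section 7.6 says the toxicity ranges were identical from protocol v4.0 through v6.0. The changes it lists after v3.0 concern lipids, prothrombin time, activated PTT and urine blood, not phosphorus. Version 3.0, which governs samples taken before 23DEC2019, is not among the documents, so its phosphorus row is unseen.

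**How many results are exposed?** By plan, Cohort 1 has 4 subjects and Cohort 2 has 8, so 4 + 8 = 12. Scheduled post-dose chemistry is on Days 2, 7 and 30, so 12 × 3 = 36 scheduled post-dose results at planned enrolment, plus any unscheduled ones. The documents do not say whether any of them was 2.0.

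**The case against.** **The value is not lost.** A reader might infer that a 2.0 would be reported as no toxicity or would drop out of the report. The documents do not support that. Table 16 and Listing 11 would still print the result, marked ONR. Only the graded summary omits it.

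**The halting rules.** A reader might also infer that the gap would make a halting rule fail. That does not follow. Sections 8.7.1 and 8.7.2 count adverse events judged related, in 2 or more subjects of a cohort or 5 or more in the study; the sentinel rule can act on one subject but needs a related event that has not resolved within 72 hours of onset. Severity and relationship are assessed at the site (Section 8.1.1), and the halting report is built from data entered in EDC (Section 3.1.3). Nothing says that the programmed grade behind Table 20 feeds these counts. What remains is the case in which the site, using Appendix B, leaves a related 2.0 ungraded.

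**The fallback.** Section 8.6 and the Appendix B footnote say that abnormal laboratory values not listed in the appendix "will be evaluated by the study clinicians, recorded in the source document and, if clinically significant, considered AEs and graded" under Section 8.1. One can read 2.0 as a value that is not listed. However, phosphorus is a listed analyte, the wording is ambiguous, and the route depends on a judgement of clinical significance. It softens the gap for adverse-event recording and gives a grading program no rule.

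**Precision.** No section states how many decimals the laboratory reports for phosphorus. With two decimals, 2.00 to 2.09 would be ungraded, but other rows would have gaps as well (potassium 3.15, for example), and phosphorus would no longer be the only one. This objection stands as a limit on the claim.

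**Treatment emergence.** SAP Section 7.6 describes it as numerical worsening from baseline, unlike the protocol's grade-based definition. The SAP wording restricts when a grade may be assigned; it does not supply one for 2.0.

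**The trial is over.** SAP Section 1 records termination on 27APR2020 with no enrolment beyond Cohort 2, so any effect on future halting is moot. Table 20 is still to be programmed for the abbreviated report.

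**Conclusion.** The threshold is wrong as written. At one-decimal precision, 2.0 mg/dL has no grade although it is worse than a Grade 2 value, and no rule in either document clearly closes the gap. The supported consequence is omission from the graded counts and the maximum post-baseline severity in Table 20.

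The point is minor: one reportable value in one analyte, among about 36 planned scheduled post-dose results. It rests on three assumptions: phosphorus is reported to one decimal; 2.0 is below the laboratory's normal range, as a Grade 1 band reaching up to 2.4 implies; and, for samples before 23DEC2019, the v3.0 row is the same. The documents do not show which of the two adjacent grades was intended.

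**What to change.** The sponsor should reconcile the Grade 2 and Grade 3 limits so that 2.0 falls in one of the two bands, and record the decision in the SAP grading specification and the grading program. As the trial has ended, the SAP and the program are where the change has effect. The Cohort 1 and 2 data should then be searched for any phosphorus of 2.0, and any such result regraded before Tables 16 and 20 and Listing 11 are produced. The laboratory's reporting precision and the v3.0 row should be confirmed in the same step. The cost is one table cell, one line of code and one data query.

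Suggested SAP wording, with the grade left for the sponsor to supply: *A phosphorus result of 2.0 mg/dL, which Protocol Appendix B leaves between Grades 2 and 3, will be graded as [2 or 3, per sponsor decision].*

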## LIST OF ABBREVIATIONS

AE	Adverse Event/Adverse Experience
ALT	Alanine aminotransferase
AST	Aspartate aminotransferase
ATC	Anatomical Therapeutic Code
AUC	Area under the plasma concentration versus time curve
AUC inf	Area under the plasma concentration versus time curve from time 0 to infinite time
AUC last	Area under the plasma concentration versus time curve from time 0 to the time of the last quantifiable concentration
BA	Bioavailability
BMI	Body Mass Index
BP	Blood Pressure
bpm	Beats per minute
BUN	Blood Urea Nitrogen
BQL	Below Limit of Quantification
CI	Confidence Interval
CL	Total clearance
CL/F	Apparent clearance
C max	Maximum measured plasma concentration
CSR	Clinical Study Report
CV %	Coefficient of Variation
DMID	Division of Microbiology and Infectious Diseases
ECG	Electrocardiogram
GM	Geometric Mean
λ z	The terminal phase elimination rate constant
IV	Intravenous
LLOQ	Lower Limit of Quantification
MAD	Multiple Ascending Dose
Max	Maximum
MedDRA®	Medical Dictionary for Regulatory Activities
Min	Minimum
MOP	Manual of Procedures
MTD	Maximum tolerated dose
N	Number (typically refers to subjects)
NCA	Noncompartmental Analysis
PE	Physical Examination
PI	Principal Investigator
PK	Pharmacokinetics
PR (interval)	Interval measured from the beginning of the P wave to the beginning of the QRS complex in the heart's electrical cycle as measured by electrocardiogram
PT	Preferred Term
PTT	Partial Thromboplastin Time
QNS	Quantity Not Sufficient

